9.9. Source Documents

Source documents provide evidence for the existence of the patient and substantiate the integrity of the data collected. Source documents are filed at the Investigator's site.

Data entered in the eCRF that are transcribed from source documents must be consistent with the source documents or the discrepancies must be explained. The Investigator may need to request previous medical records or transfer records, depending on the study. Also, current medical records must be available. Changes or corrections to eCRFs will be made by the Investigator or an authorized member of the study staff according to the policies and procedures at the site.

9.10. Study and Site Closure

The Sponsor or designee reserves the right to close the study site or terminate the study at any time for any reason at the sole discretion of the Sponsor. Study sites will be closed upon study completion. A study site is considered closed when all required documents and study supplies have been collected and a study-site closure visit has been performed.

The Investigator may initiate study-site closure at any time, provided there is reasonable cause and sufficient notice is given in advance of the intended termination.

Reasons for the early closure of a study site by the Sponsor or Investigator may include but are not limited to:

- Failure of the Investigator to comply with the protocol, the requirements of the IRB/IEC or local health authorities, the Sponsor's procedures or GCP guidelines
- Inadequate recruitment of patients by the Investigator

• Discontinuation of further study treatment development

9.11. Publication Policy

The conditions regulating dissemination of the information derived from this study are described in the Clinical Trial Agreement. The Sponsor will comply with the requirements for publication of study results. Authorship will be determined by mutual agreement and in line with International Committee of Medical Journal Editors authorship requirements.

11. APPENDIX 1: CONTRACEPTIVE GUIDANCE

Female patients of childbearing potential must agree to take appropriate precautions to avoid pregnancy from Screening through 30 days after the last dose of study drug/treatment.

Male patients should use a condom during treatment and through 90 days after the end of systemic exposure to study treatment. If the male patient has a partner that is of child-bearing potential, the partner should also use contraception through 90 days after the end of systemic exposure to study treatment. In addition, male patients must refrain from donating sperm during the study through 90 days after the end of systemic exposure of study drug/treatment. Males who have had a vasectomy \geq 90 days from the start of treatment qualify as having met the requirement for a highly effective birth control method.

Definitions:

Woman of Childbearing Potential (WOCBP)

A woman is considered fertile following menarche and until becoming post-menopausal unless permanently sterile (see below). If fertility is unclear (e.g., amenorrhea in adolescents or athletes) and a menstrual cycle cannot be confirmed before first dose of study treatment, additional evaluation should be considered.

Women in the following categories are not considered WOCBP

- 1. Premenarchal.
- 2. Premenopausal female with 1 of the following:
 - Documented hysterectomy.
 - Documented bilateral salpingectomy.
 - Documented bilateral oophorectomy.

For individuals with permanent infertility due to an alternate medical cause other than the above, (e.g., mullerian agenesis, androgen insensitivity), Investigator discretion should be applied to determining study entry.

Note: Documentation can come from the site personnel's: review of the patient's medical records, medical examination, or medical history interview.

- 3. Postmenopausal female
 - A postmenopausal state is defined as no menses for 12 months without an alternative medical cause.
 - A high FSH level in the postmenopausal range may be used to confirm a postmenopausal state in women not using hormonal contraception or HRT. However, in the absence of 12 months of amenorrhea, confirmation with more than one FSH measurement is required.

• Females on HRT and whose menopausal status is in doubt will be required to use one of the non-estrogen hormonal highly effective contraception methods if they wish to continue their HRT during the study. Otherwise, they must discontinue HRT to allow confirmation of postmenopausal status before study enrollment.

Contraception Guidance:

NOTE: There is a potential for encorafenib to induce CYP3A4, which may reduce the effectiveness of hormonal contraception methods. Therefore, the use of at least 1 form of non-hormonal contraception is required for females of childbearing potential during participation in this study.

The contraception guidelines outlined below are adapted from the recommendations related to contraception and pregnancy testing in clinical trials guidance document (Clinical Trials Facilitation Group Guidelines 2014). Patients must agree to use highly effective methods of contraception if it is mandated locally or when, in the judgment of the Investigator, compliance with acceptable methods is likely to be suboptimal. Any of the contraceptive methods listed below are permitted on the study and should be communicated to patient and their understanding confirmed.

The following methods have been classified as being highly effective (i.e., failure rate < 1% per year when used consistently and correctly) in preventing a pregnancy:

- Complete abstinence from heterosexual intercourse during the entire period of risk associated with the study treatments; the reliability of sexual abstinence should be evaluated in relation to the duration of the clinical trial and the preferred and usual lifestyle of the patient
- Combined (estrogen and progestogen containing) hormonal contraception associated with inhibition of ovulation:
 - o Oral.
 - o Intravaginal.
 - Transdermal.
- Progestogen-only hormonal contraception associated with inhibition of ovulation:
 - o Oral.
 - Injectable.
 - Implantable.
- Intrauterine device (IUD).
- Intrauterine hormone-releasing system (IUS).

- Bilateral tubal occlusion.
- Vasectomised partner (considered highly effective provided the vasectomized male has received medical assessment of surgical success and that the male is a female patient's sole sexual partner).

Acceptable birth control methods characterized as having a failure rate of more than 1% per year include:

- Progestogen-only oral hormonal contraception, where inhibition of ovulation is not the primary mode of action.
- Male or female condom with or without spermicide.
- Cap, diaphragm or sponge with spermicide.

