- 13. Female patients of childbearing potential as described in Appendix 1, must have a negative serum β HCG test result.
- 14. Female patients of childbearing potential must agree to use methods of contraception that are highly effective or acceptable, as described in Appendix 1, and to not donate ova from Screening until 30 days after the last dose of study treatment.

15. Male patients must agree to use methods of contraception that are highly effective or acceptable, as described in Appendix 1, and to not donate sperm from Screening until 90 days after the last dose of study drug.

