6.5.1. Permitted Concomitant Therapy Requiring Caution and/or Action

6.5.1.1. CYP and UGT Substrates and Inhibitors

Encorafenib is a reversible inhibitor of CYP2B6, CYP2C9, CYP3A4 and UGT1A1. It is also a time-dependent inhibitor of CYP3A4, and induced CYP2B6, CYP2C9 and CYP3A4 in human primary hepatocytes. Permitted medications to be used with caution in this study include those that are sensitive substrates of CYP2B6, CYP2C9, CYP3A4 and UGT1A1 or those substrates that have a narrow therapeutic index.

There is a potential for encorafenib to induce CYP3A4, which may reduce the effectiveness of hormonal contraception methods. Therefore, the use of at least 1 form

of non-hormonal contraception is required for females of childbearing potential during participation in this study.

Caution should be used in patients receiving concomitant treatment with other drugs that are substrates of CYP3A4 as the efficacy of these drugs could be reduced when administered with encorafenib.

Encorafenib has been identified to be metabolized by CYP3A4 and to a lesser extent by CYP2C19 in vitro. **Concomitant use of moderate CYP3A4 inhibitors should be avoided.** If use of a moderate CYP3A4 inhibitor is unavoidable, short-term use (\leq 30 days) following discussion with the Sponsor may be permitted with an accompanying dose reduction to one-half of the encorafenib dose prior to use of the moderate CYP3A4 inhibitor. After the inhibitor has been discontinued for 3 to 5 elimination half-lives, resume the encorafenib dose that was taken prior to initiating the CYP3A4 inhibitor.

In vitro, binimetinib has been identified to be primarily metabolized by glucuronidation. Strong inducers of UGT1A1 should be taken with caution when co-administered with binimetinib.

For tabulated CYP substrates, inhibitors and inducers to be used with caution or avoided, please consult with the FDA website: Drug Development and Drug Interactions: Table of Substrates, Inhibitors and Inducers.

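### Appendix 1 is inconsistent on whether a woman on HRT with doubtful menopausal status is of childbearing potential, and pregnancy safeguards turn on the answer

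*Protocol*

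**What the plan says.** Appendix 1 of the protocol first defines a woman of childbearing potential (WOCBP): "A woman is considered fertile following menarche and until becoming post-menopausal unless permanently sterile". A list then follows under the line "Women in the following categories are not considered WOCBP". Its third item is the postmenopausal female, defined by 12 months without menses and no other medical cause.

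Two sub-bullets under that item matter here. On hormone testing: "A high FSH level in the postmenopausal range may be used to confirm a postmenopausal state in women not using hormonal contraception or HRT". On HRT: "Females on HRT and whose menopausal status is in doubt will be required to use one of the non-estrogen hormonal highly effective contraception methods". This applies where the woman wants to stay on HRT during the study. The HRT bullet closes with the alternative: "Otherwise, they must discontinue HRT to allow confirmation of postmenopausal status before study enrollment".

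The contraception guidance that comes next opens with a NOTE. It gives the same reason as Section 6.5.1.1: "There is a potential for encorafenib to induce CYP3A4, which may reduce the effectiveness of hormonal contraception methods". It concludes that "use of at least 1 form of non-hormonal contraception is required for females of childbearing potential".

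Other sections rely on the Appendix 1 classification. Criterion 13 in Section 5.1 reads "Female patients of childbearing potential as described in Appendix 1, must have a negative serum" β-HCG result. Criterion 14 asks patients of childbearing potential to agree to contraception and not to donate ova until 30 days after the last dose. Section 7.3.9.2 limits pregnancy testing to WOCBP as Appendix 1 defines them, and expressly excuses patients whom Appendix 1 classes as nonchildbearing.

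**The concern.** The HRT bullet is about women whose menopausal status is not settled, but it is filed among categories declared not to be of childbearing potential. It names a contraceptive requirement that a hormonal method can meet, and it makes no mention of the rule a few lines below that hormonal contraception should not be relied on by itself with encorafenib.

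Section 2.1.4 states that either study drug can harm a fetus. If a site takes the heading at its word, such a woman could be treated while using a method whose effectiveness the protocol itself questions, with no required negative test at baseline and no scheduled tests to find a pregnancy. Another site that works from the definition would apply every safeguard to the same patient.

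**Working it through.** No arithmetic applies. The check is to set the provisions side by side.

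1. **Placement.** The HRT bullet is the third sub-bullet of the postmenopausal item, so the heading that removes women from the WOCBP group stands over it.

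2. **Definition.** Fertility is the default until a woman becomes post-menopausal or is permanently sterile. A woman whose status is in doubt has not been shown to meet the 12-month criterion. By the definition she is WOCBP; by the list she is not. The appendix states no order of precedence.

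3. **Can the doubt persist on study?** Yes. FSH confirmation is offered only to women not using hormonal contraception or HRT. Confirmation before enrollment is tied only to the branch in which HRT is stopped. A woman who stays on HRT has no stated FSH route to settle her status.

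4. **What the bullet accepts.** The phrase about non-estrogen hormonal methods has two readings. It can mean hormonal methods without estrogen, that is, progestogen-only methods or the hormone-releasing intrauterine system. Or it can mean any highly effective method other than the estrogen-containing ones, which adds the IUD, tubal occlusion, a vasectomised partner and abstinence. The first steers her to a hormonal method; the second permits one. On both, a progestogen-only method meets the bullet's own terms.

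5. **What depends on the classification.**

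| Provision | Site follows the list heading | Site follows the definition |
|---|---|---|
| Criterion 13: negative serum test | Not required | Required |
| Criterion 14: contraception agreement, no ova donation to 30 days after last dose | Not required | Required |
| NOTE and Section 6.5.1.1: at least one non-hormonal form | Not required | Required |
| Section 7.3.9.2 and Schedule of Activities: serum tests at screening and end of treatment, urine test on Day 1 of each cycle | Excused | Required |

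The opening sentence of Appendix 1, on precautions through 30 days after the last dose, is also limited to patients of childbearing potential. Under the heading, the only contraceptive requirement left is the bullet's own.

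**The case against.** A reader might infer that the protocol lets this woman rely on a progestogen-only method alone. The documents do not support that. The bullet never says that one such method is sufficient. The definition keeps an unconfirmed woman in the WOCBP group, and the NOTE then requires a non-hormonal form as well. Meeting the bullet is not the same as meeting the protocol.

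The heading-led reading is also strained. The listed category is the postmenopausal female, not the woman in doubt. Imposing contraception makes little sense for someone already cleared, and the alternative of stopping HRT presumes that her status is still open. Appendix 1 suggests further evaluation where fertility is unclear, and Section 5 directs eligibility questions to the sponsor before enrollment.

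Some safeguards hold whatever the classification. Exclusion 20 bars pregnancy and planned pregnancy, Section 6.7 stops treatment if pregnancy occurs, Section 7.5.5.1 requires exposure to be reported within 24 hours, and Section 7.3.9.2 allows testing when medically indicated.

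This argument settles which reading is better. It does not remove the conflict. The heading is explicit, and so is the waiver of tests in Section 7.3.9.2; a site that acts on both is following printed text. The remaining safeguards work mainly once pregnancy is known or suspected, and do not replace a required baseline test or scheduled tests.

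**Conclusion.** The point holds as an internal inconsistency in Appendix 1 with a patient-safety consequence. It does not show that the protocol authorises hormonal-only contraception for these women. The intended reading is probably the protective one, but criteria 13 and 14, the non-hormonal rule and the pregnancy tests should not depend on a site looking past the heading to the definition.

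Its size cannot be put in figures. The documents do not say how many enrolled women would be on HRT with doubtful status, and they give no excess failure rate for hormonal contraception taken with encorafenib. The conclusion rests on the wording alone and on the assumption that some sites would act on the list heading. The objective response rate analysis, its power and its error rates are unaffected.

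**What to change.** Add to the HRT bullet that a woman on HRT with doubtful menopausal status is treated as WOCBP until postmenopausal status is confirmed, and that criteria 13 and 14 and the Section 7.3.9.2 pregnancy tests therefore apply to her. State also that she must use at least one non-hormonal form of contraception under the NOTE: by itself if it is highly effective, or in addition to a non-estrogen hormonal method.

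The change need not demand that the non-hormonal form be highly effective in every case. The NOTE does not ask for that, and an implant with a condom, for example, would meet both the bullet and the NOTE.

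The cost is a small wording change in Appendix 1 and in matching site materials. The downside is that a few women add a contraceptive method or have extra pregnancy tests.

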12. APPENDIX 2: RECOMMENDED DOSE MODIFICATIONS FOR ENCORAFENIB-RELATED* ADVERSE EVENTS

| Severity of Adverse Event | Dose Modifications | |
|--|--|--|
| New Primary Malignancies | | |
| Non-cutaneous RAS mutation-positive malignancies | Permanently discontinue encorafenib and binimetinib. | |
| Uveitis | | |
| Grade 1-3 | If Grade 1 or 2 does not respond to specific ocular therapy, or for Grade 3 uveitis, withhold encorafenib and binimetinib for up to 6 weeks. | |
| | If improved, resume at same or reduced dose. If not improved, permanently discontinue. | |
| Grade 4 | Permanently discontinue encorafenib and binimetinib. | |
| Other Eye Disorders (i.e., non-Uveitis Events) | | |
| Grade 1–2 | Maintain dose level of encorafenib and binimetinib and increase frequency of ophthalmic monitoring to at least every 14 days until stabilization or resolution. | |
| Grade 3 | Interrupt dosing of encorafenib and binimetinib and refer patient to ophthalmologist within 7 days. | |
| | If resolved to Grade ≤ 1 in ≤ 21 days, resume treatment at 1 reduced dose level of encorafenib and binimetinib. | |
| | If not resolved to Grade ≤ 1 in ≤ 21 days, permanently discontinue encorafenib and binimetinib and close follow-up with ophthalmic monitoring until stabilization or resolution. | |
| Grade 4 | Permanently discontinue encorafenib and binimetinib and immediate follow-up with ophthalmic monitoring until stabilization or resolution. | |
| QTc Prolongation | | |
| $QTcF > 500 \text{ ms and} \le 60 \text{ ms increase from baseline}$ | 1 st occurrence: | |
| | • Temporarily interrupt dosing of encorafenib until QTcF < 500 ms. Then resume treatment at 1 reduced dose level of encorafenib. | |
| | 2 nd occurrence: | |

| Severity of Adverse Event | Dose Modifications | |
|---|--|--|
| | • Temporarily interrupt dosing of encorafenib treatment until QTcF < 500 ms. Then resume treatment at 1 reduced dose level of encorafenib. | |
| | Permanently discontinue encorafenib and binimetinib. | |
| QTcF > 500 ms and > 60 ms increase from baseline | Permanently discontinue encorafenib and binimetinib. | |
| Hepatotoxicity | | |
| Grade 2 AST or ALT increased | Maintain encorafenib dose. | |
| | • If no improvement within 4 weeks, withhold encorafenib until improved to Grade 0-1 or to pretreatment/baseline levels and then resume at the same dose. | |
| Grade 3 or 4 AST or ALT increased | See Other Adverse Reactions | |
| Dermatologic (Except Palmar-plantar Erythrodysesthesia Syndrome) | | |
| Grade 2 | If no improvement within 2 weeks, withhold until Grade 0-1. Resume at same dose if first occurrence or reduce dose if recurrent. | |
| Grade 3 | Withhold until Grade 0-1. Resume at same dose if first occurrence or reduce dose if recurrent. | |
| Grade 4 | Permanently discontinue encorafenib and binimetinib. | |
| Hand-foot Skin Reaction (HFSR)/Palmar-plantar Erythrodysesthesia Syndrome (Dose Adjustment for Encorafenib ONLY) | | |
| Grade 1 | Maintain dose of encorafenib. Promptly institute supportive measures, such as topical therapy, for symptomatic relief. Give instruction on life-style modifications. | |
| Grade 2 | 1st occurrence: Maintain dose of encorafenib and HFSR should be closely monitored. Promptly institute supportive measures, such as topical therapy, for symptomatic relief. Give instruction on life-style modifications. If no improvement ≤ 14 days, interrupt dosing of encorafenib until resolved to Grade ≤ 1. Resume treatment with encorafenib at current dose level. Continue supportive measures, such as topical therapy, for symptomatic relief. Give instruction on life-style modifications. | |

| Severity of Adverse Event | Dose Modifications | |
|---------------------------|---|--|
| | Additional occurrence: | |
| | • Treatment with encorafenib may be maintained or interrupted based upon the Investigator's discretion. Continue supportive measures, such as topical therapy, for symptomatic relief. Give instruction on life-style modifications. | |
| | If interrupted dosing of encorafenib per Investigator's judgment, interrupt until resolved to Grade ≤ 1 . Resume treatment with encorafenib at the same dose level or 1 reduced dose level based upon the Investigator's discretion. | |
| Grade 3 | 1 st or 2nd occurrence: | |
| | Interrupt dosing of encorafenib until resolved to Grade ≤ 1. Promptly initiate supportive measures, such as topical therapy, for symptomatic relief. Give instruction on life-style modifications. Reassess the patient weekly. Then resume treatment at one reduced dose level of encorafenib. | |
| | • Consider referral to dermatologist and manage HFSR per dermatologist's recommendation. | |
| | > 3 rd occurrence: | |
| | Interrupt dosing of encorafenib until resolved to Grade ≤ 1, decision to resume treatment with encorafenib at one reduced dose level or permanently discontinue encorafenib should be based upon the Investigator's discretion. | |
| Nausea/Vomiting | | |
| Grade 1-2 | Maintain dose level of encorafenib and binimetinib. Promptly institute antiemetic measure. | |
| Grade 3 | Interrupt dosing of encorafenib and binimetinib until resolved to Grade ≤ 1 . Resume treatment at 1 reduced dose level of encorafenib. Resume treatment with binimetinib at the current dose if, in the judgment of the Investigator, the toxicity is considered to be unrelated to binimetinib, or at 1 reduced dose level. | |
| | Note: Interrupt dosing of encorafenib and binimetinib for \geq Grade 3 vomiting or Grade 3 nausea only if the vomiting or nausea cannot be controlled with optimal antiemetics (as per local practice). | |

| Severity of Adverse Event | Dose Modifications | |
|---|---|--|
| Grade 4 | Permanently discontinue encorafenib and binimetinib. | |
| Other Adverse Reactions (including renal, hemorrhage) | | |
| Recurrent Grade 2 or | Withhold for up to 4 weeks. | |
| First occurrence of any Grade 3 | If improves to Grade 0-1 or to pretreatment/baseline levels, resume at reduced dose. If no improvement, permanently discontinue encorafenib and binimetinib. | |
| First occurrence of any Grade 4 | Permanently discontinue or withhold for up to 4 weeks. | |
| | If improves to Grade 0-1 or to pretreatment/baseline levels, then resume at a reduced dose. If no improvement, permanently discontinue encorafenib and binimetinib. | |
| Recurrent Grade 3 | Consider permanently discontinuing encorafenib and binimetinib. | |
| Recurrent Grade 4 | Permanently discontinue encorafenib and binimetinib. | |

*For adverse events that may be related to both encorafenib and binimetinib, guidance is provided for the other agent also.

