13. APPENDIX 3: RECOMMENDED DOSE MODIFICATIONS FOR BINIMETINIB-RELATED* ADVERSE EVENTS

| Severity of Adverse Event | Dose Modifications | | |
|--|--|--|--|
| Cardiomyopathy | | | |
| Asymptomatic, absolute decrease in LVEF of $> 10\%$ from baseline that is also below the LLN | Withhold binimetinib for up to 4 weeks, evaluate LVEF every 2 weeks. | | |
| | Resume binimetinib at a reduced dose if the following are present: | | |
| | LVEF is at or above the LLN and Absolute decrease from baseline is 10% or less and Patient is asymptomatic. If LVEF does not recover within 4 weeks | | |
| | permanently discontinue binimetinib. | | |
| Grade 3-4 (Symptomatic congestive heart failure or absolute decrease in LVEF of $> 20\%$ from baseline that is also below LLN) | Permanently discontinue binimetinib. Closely monitor LVEF until resolution or up to 16 weeks. | | |
| Venous Thromboembolism | | | |
| Uncomplicated DVT or PE | Withhold binimetinib. | | |
| | If improves to Grade 0-1, resume at a reduced dose. If no improvement, permanently discontinue binimetinib. | | |
| Life threatening PE | Permanently discontinue binimetinib. | | |
| Serous Retinopathy | | | |
| Symptomatic serous retinopathy/ Retinal pigment epithelial detachments | Withhold binimetinib for up to 10 days. If improves and becomes asymptomatic, resume at the same dose. If not improved, resume at a lower dose level or permanently discontinue binimetinib. | | |
| Retinal Vein Occlusion (RVO) | | | |
| Any Grade | Permanently discontinue binimetinib. | | |
| Uveitis | | | |
| Grade 1-3 | If Grade 1 or 2 does not respond to specific ocular therapy, or for Grade 3 uveitis, withhold binimetinib and encorafenib for up to 6 weeks. | | |
| | If improved, resume at same or reduced dose. If not improved, permanently discontinue binimetinib. | | |
| Grade 4 | Permanently discontinue binimetinib. | | |

| Severity of Adverse Event | Dose Modifications | |
|---|--|--|
| Other Eye Disorders (i.e., Non-retinal Events, non-Uveitis Events | | |
| Grade 1-2 | Maintain dose level of encorafenib and binimetinib and increase frequency of ophthalmic monitoring to at least every 14 days until stabilization or resolution. | |
| Grade 3 | Interrupt dosing of encorafenib and binimetinib and refer patient to ophthalmologist within 7 days. | |
| | • If resolved to Grade ≤ 1 in ≤ 21 days, resume treatment at 1 reduced dose level of encorafenib and binimetinib. | |

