| Other Adverse Reactions | | |
| Recurrent Grade 2 or First occurrence of any Grade 3 | Withhold for up to 4 weeks. If improves to Grade 0-1 or to pretreatment/baseline levels, resume at reduced dose. If no improvement, permanently discontinue binimetinib and encorafenib. | |
| First occurrence of any Grade 4 | Permanently discontinue or withhold for up to 4 weeks. If improves to Grade 0-1 or to pretreatment/baseline levels, then resume a reduced dose. If no improvement, permanently discontinue binimetinib and encorafenib. Consider permanently discontinuing binimetinib at | |
| | encorafenib. | |

| Severity of Adverse Event | Dose Modifications |
|---------------------------|--|
| Recurrent Grade 4 | Permanently discontinue binimetinib and encorafenib. |

*For adverse events that may be related to both binimetinib and encorafenib, guidance is provided for the other agent also.

14. APPENDIX 4: ADVERSE EVENTS: DEFINITIONS AND PROCEDURES FOR RECORDING, EVALUATING, FOLLOW-UP, AND REPORTING

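### For a Grade 1-3 RVO or symptomatic serous retinopathy/RPED possibly related to both drugs, Appendices 2 and 3 of the Protocol give different binimetinib instructions, and neither is said to prevail

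*Protocol*

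**What the plan says.** Appendix 2 of the Protocol (encorafenib-related events) has two eye categories: uveitis, and a residual row headed "Other Eye Disorders (i.e., non-Uveitis Events". It has no retinal row, so RVO and serous retinopathy/RPED fall into the residual one. At Grade 1-2 that row says "Maintain dose level of encorafenib and binimetinib and increase frequency of ophthalmic monitoring to at least every 14 days". At Grade 3 both drugs are interrupted and the patient is referred to an ophthalmologist within 7 days. If the event resolves to Grade 1 or less within 21 days, the instruction is to "resume treatment at 1 reduced dose level of encorafenib and binimetinib"; otherwise both drugs stop permanently. At Grade 4 both stop permanently.

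Appendix 3 (binimetinib-related events) words its residual row more narrowly: "Other Eye Disorders (i.e., Non-retinal Events, non-Uveitis Events". The retinal events it takes out have separate rows. Under "Retinal Vein Occlusion (RVO", any grade means permanent discontinuation of binimetinib. For symptomatic serous retinopathy/RPED, with no split by grade, the row says "Withhold binimetinib for up to 10 days. If improves and becomes asymptomatic, resume at the same dose". If there is no improvement, binimetinib resumes at a lower level or stops permanently. Neither retinal row mentions encorafenib.

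Both appendices foresee shared attribution. The Appendix 2 footnote reads "For adverse events that may be related to both encorafenib and binimetinib, guidance is provided for the other agent also", and Appendix 3 carries the same footnote with the drugs in reverse order.

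**The concern.** The two drugs are given together, so an investigator may well judge a retinal event possibly related to both. That investigator finds a matching row in each table, and each row gives a binimetinib instruction. At Grade 1-2 one keeps binimetinib going where the other stops or withholds it.

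Low-grade events can be found: Section 7.3.5.1 requires additional retinal testing when an abnormality of any grade is suspected, and it names RPED and RVO.

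At Grade 3 symptomatic serous retinopathy/RPED the choice of row can have a lasting effect. The Appendix 2 route lowers binimetinib by one level on resumption, and Section 6.6.2 bars re-escalation of either drug after a reduction for ocular toxicity of Grade 2 or more. The Appendix 3 route can return binimetinib to the dose the patient was on.

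**Working it through.** The plan states no figure on this point, so the main check sets the instructions side by side. Binimetinib action for an event possibly related to both drugs:

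| Event and grade | Appendix 2, residual eye row | Appendix 3, named row | Agree? |
|---|---|---|---|
| RVO, Grade 1-2 | Maintain | Stop permanently | No |
| RVO, Grade 3 | Interrupt; resume one level lower if Grade 1 or less within 21 days; otherwise stop | Stop permanently | No |
| RVO, Grade 4 | Stop permanently | Stop permanently | Yes |
| Symptomatic serous retinopathy/RPED, Grade 1-2 | Maintain | Withhold up to 10 days | No |
| Symptomatic serous retinopathy/RPED, Grade 3 | Interrupt; resume one level lower if Grade 1 or less within 21 days; otherwise stop | Withhold up to 10 days; same dose if improved and asymptomatic; otherwise lower or stop | No (resumption dose and time limit) |

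**Search for a precedence rule.**
- Sections 6.6.1 and 6.6.2 send the investigator to labeled and/or institutional guidance. Section 6.6.1 adds clinical judgment. Both then cite Appendices 2 and 3 together without ranking them.
- Section 6.7 requires discontinuation for Grade 4 or life-threatening events as outlined in the appendices. It does not settle a Grade 1-3 event that is not life-threatening.
- The footnotes say that guidance is given for the other agent. They do not say whose guidance wins.

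**Dose effect of the Appendix 2 Grade 3 route.** From the starting doses, Tables 7 and 8 give encorafenib 450 to 300 mg QD (300/450 = 0.667) and binimetinib 45 to 30 mg BID (30/45 = 0.667). The Appendix 3 row can return binimetinib to 45 mg BID.

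**How many patients.** The minimum treated is 60 + 37 = 97, and no more than 107 are expected (Section 8.2). Section 2.1.4 gives melanoma rates of 8% for symptomatic serous retinopathy and 0.1% for RVO. That these carry over to NSCLC is an assumption.

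- Expected symptomatic serous retinopathy: 0.08 × 97 = 7.76; 0.08 × 107 = 8.56. Central 95% binomial range: 3-13 at n = 97, 4-14 at n = 107.
- Expected RVO: 0.001 × 97 = 0.097; 0.001 × 107 = 0.107. Chance of at least one: 1 − 0.999^97 = 9.2%; 1 − 0.999^107 = 10.2%.

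These counts cover all attributions and all grades. Only Grade 1-3 cases attributed to both drugs meet the conflict, and the documents give neither that share nor a grade split.

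**The case against.** The strongest reply is that a sensible reader already knows what to do. Both appendices are titled as recommendations, and Section 6.6 points first to the label, institutional guidance and judgment about relatedness. Section 2.1.4 describes serous retinopathy and RVO as class effects of MEK inhibitors, which makes Appendix 3 their natural home. Its retinal rows say nothing about encorafenib, which suggests that the authors saw these as binimetinib events. A named row ordinarily beats a residual one. RVO is rare, and exclusion criterion 11 keeps out patients with RVO history or current risk factors.

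All of this lowers the practical impact. None of it is a written rule for choosing between the rows, and that the specific row prevails is an inference the text leaves to each site.

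A second objection concerns the remedy. The tempting repair is to add the non-retinal exclusion to the Appendix 2 heading, as in Appendix 3. That would do harm. For these events it would remove the Appendix 2 encorafenib action, the 14-day monitoring, the 7-day referral and the Grade 4 stop, and it would leave other retinal events with no eye row in either table. Likewise, applying Appendix 3 whatever the attribution would change the rule for events attributed to encorafenib alone, where no two-table conflict exists. This objection stands, and the fix below avoids both changes.

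**Conclusion.** The inconsistency is real and narrow: RVO or symptomatic serous retinopathy/RPED, Grade 1-3, possibly related to both drugs. In that setting the tables give different binimetinib instructions and no stated rule chooses between them. It is a minor safety correction. It affects few patients, subject to the assumption that the melanoma rates carry over, and it touches no endpoint, power or alpha figure.

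Three stronger readings are not supported. A reader might infer that the Protocol directs continued binimetinib after RVO; it does so only if the Appendix 2 row is followed in preference to a named row that says the opposite. A reader might infer that the encorafenib instructions also clash; the Appendix 3 retinal rows are silent on encorafenib, so nothing contradicts Appendix 2 there. And a reader might take the 8-9 expected cases as patients facing conflicting instructions; they are the expected total before restriction to Grade 1-3 events with shared attribution.

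Whether a symptomatic event can be Grade 1 depends on CTCAE wording that is not in the documents. The Grade 2 and Grade 3 differences do not depend on it.

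**What to change.** Leave the Appendix 2 heading as it is and add one note under that row, along these lines:

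*For events that may be related to both drugs, the Appendix 3 row governs binimetinib for RVO (any grade) and for symptomatic serous retinopathy/RPED of Grade 1-2. This row continues to govern encorafenib, ophthalmic monitoring and referral, all other retinal events, and permanent discontinuation at Grade 4.*

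In the same note the sponsor should state which binimetinib resumption rule applies to Grade 3 symptomatic serous retinopathy/RPED. This is a medical decision that a wording rule should not make by default. Appendix 3 is the less restrictive path, and the Appendix 2 reduction cannot be reversed under Section 6.6.2.

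The cost is one note, by amendment or clarification letter, and one sponsor decision. Endpoints and sample size are unaffected.
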